9.7.1 Primary analysis

Distribution of all possible answers

As some questions may have multiple choices or be opened fields, the proportion of HCPs/patients having provided each possible answer will be described (Table 4).

Table 4: Mock table: Distribution of HCPs/patients answers to Question XX by country and physician specialty

Specialty	Answer	Country			Overall unweighted n(%)	Overall weighted * %
		Country 1 (N=XX)	Country 2 (N=XX)	...		
GP (N=XX)	Answer 1	xx (xx.xx)	xx (xx xx)	xx (xx xx)	xx (xx xx)	xx xx
	Answer 2	xx (xx.xx)	xx (xx xx)	xx (xx xx)	xx (xx xx)	xx xx
	...	xx (xx.xx)	xx (xx xx)	xx (xx xx)	xx (xx xx)	xx xx
	Missing	xx	xx	xx	xx	-
Endocrinologist (N=XX)	...	xx (xx.xx)	xx (xx xx)	xx (xx xx)	xx (xx xx)	xx xx
Internist (N=XX)	...	xx (xx.xx)	xx (xx xx)	xx (xx xx)	xx (xx xx)	xx xx
Gastroenterologist (N=XX)	...	xx (xx.xx)	xx (xx xx)	xx (xx xx)	xx (xx xx)	xx xx
Other (N=XX)	...	xx (xx.xx)	xx (xx xx)	xx (xx xx)	xx (xx xx)	xx xx
Overall unweighted (N=XX)	Answer 1	xx (xx.xx)	xx (xx xx)	xx (xx xx)	xx (xx xx)	xx xx
	Answer 2	xx (xx.xx)	xx (xx xx)	xx (xx xx)	xx (xx xx)	xx xx
	...	xx (xx.xx)	xx (xx xx)	xx (xx xx)	xx (xx xx)	xx xx
	Missing	xx	xx	xx	xx	-
Overall weighted	Answer 1	xx xx	xx xx	xx xx	xx xx	xx xx
	Answer 2	xx xx	xx xx	xx xx	xx xx	xx xx
	...	xx xx	xx xx	xx xx	xx xx	xx xx

* According to the distribution of HCPs in the general population by country and specialty, respectively.

Note: This template might be modified, final table shells will be presented in the statistical analysis plan (SAP).

Definition of success

Three success factors for professionals treating patients with SULIQUA will be defined:

1. Proportion of HCPs receiving the EMs (Question Q1 of HCP questionnaire).
2. Proportion of HCPs sufficiently understanding the key messages, i.e. providing at least 75% of correct answers (Questions Q3-Q4, Q7 of HCP questionnaire; at least 11 correct or consistent answers out of 14 sub-questions).
3. Proportion of HCPs adequately implementing the EMs, i.e. providing at least 75% of answers that are correct or consistent with appropriate use of the EMs (Questions Q2a-b, Q5-Q6 of HCP questionnaire; at least 12 correct or consistent answers out of 15 sub-questions).

Three success factors for patients/caregivers will be as follows:

1. Proportion of patients/caregivers receiving the EM (Question Q5 of Patient/Caregiver questionnaire).

2. Proportion of patients/caregivers sufficiently understanding the key message, i.e. providing at least 75% of correct answers (Questions Q3 and Q4 of Patient/Caregiver questionnaire; at least 8 correct answers out of 10 sub-questions).
3. Proportion of patients/caregivers adequately implementing the EM, i.e. providing at least 75% of correct or appropriate answers (Questions Q6 and Q7 of Patient/Caregiver questionnaire; at least 6 correct or appropriate answers out of 8 sub-questions).

In order to allow better decision making on the eventual subsequent actions, the success rates will be evaluated separately for HCPs and patients/caregivers. The RMM will be deemed as effective based on the following definitions:

- For HCPs: if at least 2 of the 3 pertaining proportions above are equal to or above 80%
- For patients/caregivers: if at least 2 of the 3 pertaining proportions above are equal to or above 80%

Profile of HCPs with incorrect answers

The profile of HCPs with incorrect answers to the questions related to the 3 success factors will be described using all available and relevant HCPs characteristics collected in the survey (country, specialty, duration of practice, type of setting) and past experience with SULIQUA.

Profile of patients with inappropriate answers

The profile of patients with inappropriate answers to the questions related to the 3 success factors will be described using all available and relevant HCPs characteristics collected in the survey (country, treating physician's specialty, gender, age, location).

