9.7 DATA ANALYSIS

The statistical analyses will be described and further detailed into a Statistical Analysis Plan (SAP). The described analysis below might be revised, and adjustments might occur. The final SAP version will include (empty) table shells to be populated for the clinical study report (CSR).

General considerations:

The statistical analysis will be conducted using the SAS[®] software V9.4 on Windows[™] (SAS Institute, North Carolina, US).

Continuous variables will be described by their number (of valid cases, of missing values), mean, standard deviation, median, Q1, Q3, minimum and maximum. Categorical variables will be described as the total number and relative percentage per category. Confidence intervals of 95% will be evaluated, when relevant. The number of missing data will be indicated. Since, missing values are expected to be few and distributed at random, no replacement or imputation will be performed. Missing values will not be considered in the denominators for proportions.

For HCP questionnaire measures, results will be stratified by country and physician's specialty. For patient questionnaire measures, results will be stratified by country and treating physician's specialty. In tables "Overall - unweighted" columns and lines will show the results observed on the sample while "Overall weighted" columns and rows will show the results weighted according to the distribution of HCPs in the general population by country and specialty, respectively.

Two interim and 1 final analysis corresponding to 3 waves of survey will be performed according to timelines (Section 6) in selected European countries.

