2	Guide for patients and/or caregivers	 Yes  No  I do not remember
3	Letter - Important prescribing information	 Yes  No  I do not remember

Data: single punch per row

Ask Q2a only if response to 1 is yes

Ask Q2b only if response to 2 is yes

Key message:

Sanofi should deliver educational material to Healthcare professionals according to the additional risk minimization measures described in the Suliqua Risk Management Plan.

Q2a. Please answer to the following questions related to the use of the Guide for Healthcare Professionals:

	Use of educational materials	
1	Do you review the HCP guide checklist when prescribing/dispensing Suliqua to a patient for the first time ?	 Never  Occasionally  Frequently
2	Do you review the HCP guide checklist when changing Suliqua pen strength to a patient for the first time ?	 Never  Occasionally  Frequently
3	Do you review each point of the checklist?	 Never  Occasionally  Frequently

Data: single punch per row

Key message:

HCPs should review the checklist that is in the guide to Healthcare professional when you prescribe /deliver Suliqua pens.

Q2b. Please answer to the following question related to the use of the Guide for patients and/or caregivers:

	Use of educational materials	
	Do you provide patients with patient guide prior initiating Suliqua	 Never  Occasionally  Frequently

Data: single punch per row

Key message:

HCPs should provide patients with the patient guide prior to prescribing or dispensing Suliqua.

Q3. According to your knowledge about the dose titration of Suliqua, which of the following statements are true and which are false?

	Prescription /Patient first daily dose/ dosage titration	TRUE	FALSE
1	Insulin-naive patients (on oral antidiabetic only), should start with 10 dose steps daily.	()	()
2	Patients who received between 20 and 30 units of insulin, should start with 30 dose steps daily.	()	()
3	Patients who received insulin or insulin glargine twice a day, should have a reduction of total daily dose of Suliqua by 10%.	()	()

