4	For doses >40 dose steps/day titration must be continued with Suliqua (30-60) pen.	()	()
5	For total daily doses >60 dose steps/day, Suliqua must not be used.	()	()

Data: single punch per row

Answer:

Option 2 is wrong (patient had insulin before between 20 and 30 units, patient should start with 20 dose steps

Option 3 is wrong (Patients who received insulin or insulin glargine twice a day, should have a reduction of total daily dose of Suliqua by 20%)

Key message:

Prescriber /Pharmacist should understand and know the table in HCP guide for starting dose

Q4. According to your knowledge about the two different Suliqua pens, which of the following statements are true and which are false?

	Prescription/ Pen choice	TRUE	FALSE
1	Patient can use the colour of pen of his/her choice	()	()
2.	The Suliqua (10-40) pen allows a daily injection of doses between 10 and 40 dose steps	()	()
3	The Suliqua (30-60) pen allows a daily injection of doses between 30 and 60 dose steps	()	()
4	The Suliqua pen (30-60) is olive coloured with a brown button	()	()
5	Both pre-filled pens contain insulin glargine in a strength of 100 Units/mL	()	()

Data: single punch per row

Answer:

Option 1 is wrong (patient should use the pen according to the dose steps that he/she will be prescribed).

Key message:

Prescriber /Pharmacist should understand and know the table in HCP guide for starting dose

Q5. According to your knowledge related to the communication with the patients, what important message(s) should be provided to the patient? (you can select more than one answer)

	Education of patient	
1	Patients should use the same needle for several injections	()
2	Patients should closely monitor their blood sugar level when starting Suliqua which contains insulin glargine 100U/ml and lixisenatide (non insulin substance)	()
3	The dose pointer shows the number of dose steps to be injected	()
4	Patients should read the patient guide and the patient information leaflet, as well as the leaflet provided in Suliqua Solo Star packaging carefully.	()
5	Patients who are blind or have low vision should be helped by another person who has been trained on Suliqua use	()
6	The peach colour pen and the olive colour pen contain the same concentration of insulin	()
7	Patients should report any side effect/medication error to their doctor or pharmacist	()

Data: multiple punch

Option 1 incorrect

Key message:

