HCP should refer to the HCP material and checklist to inform patient about specificities of the pen use.

Q6. According to your knowledge what should be the important information to be indicated in the prescription for Suliqua? (you can select more than one answer)

	Prescription	
1	Number of dose steps to be injected	()
2	Strength of pen	()
3	Name of product	()
4	Associated dose range /strength	()

Data: multiple punch

Answer: mandatory: 1,3,4;

Key message

The prescription should mention which pre-filled pen type you need (the SULIQUA [100 units/mL + 50 micrograms / mL] pen or the SULIQUA [100 units/mL + 33micrograms / mL] pen) and the number of dose steps to be injected.

Q7. According to your knowledge, which of the following Suliqua safety messages should be communicated to patients treated with Suliqua ? (you can select more than one answer)

	Safety messages	
1	Patients may experience side effects and should talk to their doctors or pharmacists	()
2	Patients may develop osteosarcoma and should be monitored for bone pain and swelling	()
3	Medication errors are the most common cause of adverse events and patients should ask, if needed, clarifications on how to use their pen and on how many dose steps they require	()

4	Patients may experience dysglycemia and should measure their blood sugar more frequently in the weeks after the shift to Suliqua	()
---	--	-----

Data: multiple punch

Answer: Option 2 is wrong

Key message:

HCPs should explain that the patient should anticipate dysglycemia and potential adverse reactions.

Q8. According to your experience, which of the following are the most relevant sources of information that should guarantee appropriate use of Suliqua by patients? (you can select more than one answer)

	Source of information	
1	Patient guide	()
2	Patient leaflet and instructions for use accompanying the pen	()
3	Explanations from prescribing physician	()
4	Explanations from delivering pharmacist	()
5	Explanations from a nurse	()
6	Other (ie: Patient group experience, internet, ..)	()

Data: multiple punch

Q9 and Q10 for prescribers [D2a=1 or 2 or 4 or 5]

Q9. How many prescriptions for Suliqua have you been queried about or have been returned for clarification by dispensers / pharmacists in the last 3 months?

1	None (0)	()
2	1-5	()
3	6-10	()
4	11-20	()
5	>20	()

Data: Single punch

Q10 How many prescriptions for Suliqua have you been queried about or have you been asked for clarification by patients in the last 3 months?

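### HCP success factor 3 fixes 12 of 15 points, but up to 4 of the 15 items are routed out by guide receipt, so the cut-off does not mean 75% and the factor is capped by receipt

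*Protocol*

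**What the plan says.** Protocol section 9.7.1 defines HCP factor 3 as "Proportion of HCPs adequately implementing the EMs, i.e. providing at least 75% of answers that are correct or consistent with appropriate use of the EMs", built from Q2a-b and Q5-Q6, and turns the percentage into a count: "at least 12 correct or consistent answers out of 15 sub-questions". Factor 1 is "Proportion of HCPs receiving the EMs (Question Q1 of HCP questionnaire"). The measures are judged effective for HCPs when at least two of the three proportions reach 80%.

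The HCP questionnaire in Annex 2 carries two routing instructions after Q1: "Ask Q2a only if response to 1 is yes" and "Ask Q2b only if response to 2 is yes". Q1 also offers a no and a not-remembered answer, and both skip the follow-up. Receipt is not an eligibility condition in section 9.2.2 or in the screener, so HCPs without a guide stay in the survey.

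The general rule in section 9.7 is "Missing values will not be considered in the denominators for proportions". It does not mention items skipped by design.

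**The concern.** A fixed count works as a percentage only if everyone is asked the same number of items. Here the number asked depends on receipt, which is itself factor 1. An HCP routed past Q2a and Q2b who answers every remaining item correctly has given 100% correct answers and so meets the stated percentage, yet fails the stated count. The two halves of one definition disagree.

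At stake is the primary success rule. If HCPs without a guide count as failures, low receipt pulls down factor 3 as well as factor 1, and two of the three factors can fail for one reason. If factor 3 is read among recipients only, the same data can give the opposite verdict. The protocol does not say which is meant.

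**Working it through.** **Reproducing the plan's figure.** Counting rows in Annex 2: Q2a 3 + Q2b 1 + Q5 7 + Q6 4 = 15. 75% of 15 is 11.25, rounded up to 12. The stated 12 of 15 is correct for an HCP who is asked everything.

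**Maximum score by routing path.** Q5 and Q6 (7 + 4 = 11 items) are asked of all; Q2a adds 3 and Q2b adds 1.

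| Guides received | Items asked (maximum) | Cut-off 12 as a share | 75% of items asked, rounded up |
|---|---|---|---|
| Both | 11 + 3 + 1 = 15 | 12/15 = 80% | 12 |
| HCP guide only | 11 + 3 = 14 | 12/14 = 86% | 11 |
| Patient guide only | 11 + 1 = 12 | 12/12 = 100% | 9 |
| Neither, or not remembered | 11 | unreachable | 9 |

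This takes all four Q6 items as scored, which the total of 15 requires. The answer key for Q6 reads "Answer: mandatory: 1,3,4". If item 2 earned no point, the maxima would fall by one each, to 14, 13, 11 and 10. The mismatch would remain.

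**Effect on one HCP's chance of passing.** Assume each item is answered correctly with probability 90%, independently. The chance of at least 12 correct is 94% with 15 items, 84% with 14, 28% with 12 and 0% with 11.

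**Effect on the verdict.** The documents give no receipt or implementation rate (the abstract says the proportion who received and understood the material is unknown), so the inputs below are assumed. Let R be the share who received both guides, the rest neither, with factor 1 equal to R; and let I be the share of recipients reaching 12 of 15. Then factor 3 over all HCPs is R × I, and among recipients it is I.

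- R = 70%, I = 95%, understanding 85%: 0.70 × 0.95 = 66.5% over all HCPs, so one of three factors reaches 80% (not effective). Among recipients it is 95%, so two of three (effective).
- R = 85%, I = 90%, understanding 75%: 0.85 × 0.90 = 76.5% (not effective) against 90% (effective).
- For factor 3 to reach 80% over all HCPs, R must be at least 0.80/I: 94.1%, 88.9% or 84.2% for I = 85%, 90% or 95%.

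**At the planned wave size of 128 analysable HCPs (section 9.5.1).** Suppose 96 receive both guides (75.0%), 86 of these pass, and understanding is 85%. Factor 3 is 86/128 = 67.2% over all HCPs and 86/96 = 89.6% among recipients. A pro rata rule applied to everyone (9 of 11 for those with no guide, with about 29 of 32 passing) gives 115/128 = 89.8%, but it credits HCPs who hold no guide with implementing it. In a simulation with true receipt 75%, implementation 90% and understanding 88%, all independent, the probability of an effective verdict was about 9% over all HCPs and 99% among recipients.

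**Where the reading does not matter.** If receipt and understanding are both at or above 80%, two factors already pass. If both are below 80%, at most one can pass. The verdict is then the same on either denominator.

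**The case against.** The best defence is that the cap is intended. An HCP who never had a guide cannot implement it, section 9.7.1 speaks of a proportion of HCPs without restricting it to recipients, and section 8 states the objective jointly as receiving, understanding and implementing. On that view, a failed verdict when many prescribers never got the material is sensible and conservative. This stands: counting such HCPs as not implementing is a defensible reading.

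The defence does not cover partial recipients. An HCP with only the patient guide must be perfect, and one with only the HCP guide needs 86%, although the text says 75%.

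A second defence is that section 9.7 leaves detail to the SAP and allows revision. Scoring of not-applicable items could well be settled there. But the protocol itself fixes a count that conflicts with its own questionnaire, and that conflict is the point.

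Three stronger readings are tempting and not supported:
- A reader might infer that anyone missing a guide fails automatically. Only those with neither guide, or remembering neither, cannot reach 12.
- A reader might infer that the missing-value rule in section 9.7 removes HCPs without a guide from the denominator. They have answered all of Q5 and Q6. That rule also rests on missing values being few and random, which items skipped by design are not.
- A reader might infer that factor 3 must be restricted to HCP-guide recipients. That would drop HCPs holding only the patient guide, who are asked Q2b, and would make success easier after Wave 1 began.

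**Conclusion.** The point holds as a contradiction inside a stated decision threshold. The count of 12 equals 80%, 86%, 100% or an unreachable share of the items asked, depending on receipt, while the definition says 75%. Over all HCPs, factor 3 is bounded by the share who received at least one guide, so receipt enters two of the three factors.

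The choice of denominator can reverse the verdict, as in the 66.5% against 95% example. It does so only when receipt and understanding fall on opposite sides of 80%, and then only for some implementation rates. The ceilings follow from counting items and assume that all four Q6 items score; the size of any effect on the verdict rests on assumed rates. The documents do not show that the all-HCP reading is wrong. They leave it unstated, and the choice should not be made after results are seen.

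**What to change.** In section 9.7.1, replace the fixed count with at least 75% of the items presented: 12 of 15, 11 of 14, or 9 of 12. State that routed-out items are not applicable and do not fall under the missing-value rule of section 9.7. State before analysis that HCPs who received neither guide, or remember neither, count as not implementing in the all-HCP figure. Report beside it the figure among HCPs who received at least one guide.

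Name which of the two enters the 2-of-3 rule. Keeping all HCPs matches the present wording; receipt then still acts on two factors, but as a declared choice.

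The cost is a few sentences and one extra table row, with no new data. The downsides are a success criterion clarified after Wave 1 recruitment started in September 2019, a somewhat lower bar for partial recipients, and a smaller denominator for the recipients' figure.

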9.10 OTHER ASPECTS

Strengths of the research methods:

1. The information contained in the file of each country is updated constantly with proactive updates. Quality controls are implemented on a regular basis.
2. The sampling of HCPs follows a stratified randomized method which guarantees the representativeness of the contacted population in order to limit selection bias due to voluntary participation. Batches of HCPs will be contacted up to five times before moving forward to other HCPs in the lists.
3. The questionnaires include general questions followed by specific ones in order to limit a learning process during the survey. As the HCPs may understand the right answer in subsequent questions, it will not be possible to go back in the questionnaire and edit answers in former questions.
4. The questionnaires are tested for clarity. It is also checked whether there are questions which would suggest a specific answer for any reason e.g. social desirability. The translations of the questionnaires are tested before implementation.
5. The study is conducted by an experienced team specialised in the design and conduct in such survey in safety area. The study follows IQVIA SOPs as well as the methodological guidelines from European Network of Centres for Pharmacoepidemiology and Pharmacovigilance (ENCePP) and EMA GVP.

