1	The dose pointer of the pen shows the number of dose steps to be injected	()	()
2	1 dose step of Suliqua contains 1 unit of insulin glargine 100U/ml plus a corresponding amount of lixisenatide	()	()
3	Even when the needle is changed, the pen should not be used by another person	()	()
4	You cannot use a syringe to withdraw Suliqua from a pre-filled pen	()	()
5	It is important to closely monitor your blood sugar level when starting Suliqua	()	()
6	One dose step of Suliqua only states the amount of lixisenatide	()	()

Data: single punch per row

Answer: Option 6 is false.

Q4. According to your knowledge, which of the following statements are true and which are false?
 Please select one answer per row.

		TRUE	FALSE
1	The prescription should mention which pre -filled pen you should use	()	()
2	The Suliqua (10-40) pen allows a daily injection of doses between 10 and 40 dose steps	()	()
3	The Suliqua (30-60) pen allows a daily injection of doses between 30 and 60 dose steps	()	()
4	If my total daily dose is more than 60 dose steps, then I should not use any of the Suliqua pens	()	()

Data: single punch per row

If S4=1 then skip item 3

If S4=2 then skip item 2

If S4= 3 then keep item 2 and item 3

Answer: All is true

Q5. Have you - or has the person you take care of - received the Suliqua Patient Guide from your physician or pharmacist? Please select one answer

Yes No

Data: single punch

Q6. Have you - or has the person you take care of - read the following educational materials (EM) related to Suliqua before using Suliqua? Please select one answer per row.

1	Suliqua Patient Guide (information that you may have received from your physician or pharmacist)	 Yes  No
2	Patient Information Leaflet (information available in each pack of Suliqua pre-filled pen)	 Yes  No

Data: single punch per row

If Q5=2 then skip item 1

Q7. Where would you - or the person you take care of - look for additional information if you have difficulties in understanding the prescription or use of the Suliqua pen ? You can select more than one answer.

	Prescription/ missing information	
1	Ask a physician	()
2	Ask a pharmacist	()
3	Ask a nurse	()
4	Read the Information Leaflet from the Suliqua package	()
5	Read the Suliqua Patient Guide	()
6	Read on the web	()

Data: multiple punch
If Q5=2 then skip item 5

Answer: all is true

Note :

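### Patient understanding factor: nine of the ten scored statements are keyed true, so a patient who ticks TRUE throughout always passes

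*Protocol*

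**What the plan says.** Section 9.7.1 of the protocol (Definition of success) gives patients and caregivers three success factors. The second is "Proportion of patients/caregivers sufficiently understanding the key message, i.e. providing at least 75% of correct answers", which is then fixed as "Questions Q3 and Q4 of Patient/Caregiver questionnaire; at least 8 correct answers out of 10 sub-questions". The measure is deemed effective for patients if at least two of the three factors reach 80%.

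Annex 3 prints the items and the key. Q3 has six statements and Q4 has four, each with only TRUE and FALSE as response options. The key for Q3 is "Answer: Option 6 is false", which leaves the other five true. The key for Q4 is "Answer: All is true".

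Two skip rules depend on screening question S4 (which pen is used): "If S4=1 then skip item 3" and "If S4=2 then skip item 2". A patient who names a pen sees nine scored statements. A patient who does not know the pen sees all ten.

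Section 9.10 lists as a strength that the questionnaires are tested for clarity, and adds: "It is also checked whether there are questions which would suggest a specific answer for any reason e.g. social desirability". It says nothing about the balance between true and false statements in the key.

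**The concern.** People who answer true/false statements about a medicine may agree with whatever sounds sensible. A knowledge score guards against this by including enough false statements that agreement alone does not reach the pass mark. Here there is one false statement in ten, and the pass mark allows two errors in ten. The patient who understands the guide and the patient who agrees with everything are then counted alike.

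Knowledge and understanding is the main objective in section 8, and this factor is one of three that decide whether the patient measure is called effective. Passes earned by agreement can only raise the proportion counted as understanding, so the error favours the finding that the guide worked. It decides the outcome when exactly one of the other two patient factors reaches 80%.

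**Working it through.** **Inputs.** Pass mark: 8 of 10, described as 75% (section 9.7.1). Key: Q3 has 5 true and 1 false, Q4 has 4 true and 0 false (Annex 3). Skip rules: one true-keyed Q4 item is removed when a pen is named (Annex 3).

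**The plan's own figure.** 6 + 4 = 10 sub-questions, and 0.75 × 10 = 7.5, rounded up to 8. The stated mark is reproduced.

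**All-TRUE score in each path.** The score is the number of true-keyed items shown.

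| Answer to S4 | Items shown | All-TRUE score | Fixed mark of 8 | 75% of items shown |
|---|---|---|---|---|
| Peach pen | 5 + 1 + 3 = 9 | 8 (88.9%) | pass | pass (7 needed) |
| Green pen | 5 + 1 + 3 = 9 | 8 (88.9%) | pass | pass (7 needed) |
| Not known | 5 + 1 + 4 = 10 | 9 (90%) | pass | pass (8 needed) |

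For nine items, 0.75 × 9 = 6.75, rounded up to 7.

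**What the factor does screen out.** An all-FALSE responder scores 1 and fails. A responder guessing each item with probability 0.5 passes with probability:

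- ten items, mark 8: (45 + 10 + 1)/1024 = 5.5%
- nine items, mark 8: (9 + 1)/512 = 2.0%
- nine items, mark 7: (36 + 9 + 1)/512 = 9.0%

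**How many all-TRUE responders would matter.** If a share *a* answer all-TRUE and a proportion *u* of the others pass, the factor equals *a* + (1 − *a*)*u*. It reaches 0.80 when *a* = (0.80 − *u*)/(1 − *u*). The values of *u* below are assumptions.

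- *u* = 0.60: *a* = 0.20/0.40 = 50%
- *u* = 0.70: *a* = 0.10/0.30 = 33%
- *u* = 0.75: *a* = 0.05/0.25 = 20%

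**How many false-keyed items would close the gap.** This keeps the pass mark and places the false items among those shown to everyone.

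| False-keyed items | All-TRUE, 10 shown | All-TRUE, 9 shown |
|---|---|---|
| 1 (as planned) | 9, pass | 8, pass |
| 2 | 8, pass | 7, fails a fixed 8 but passes 75% |
| 3 | 7, fail | 6, fails both readings |

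Three is the smallest number for which all-TRUE fails in every path.

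**The case against.** The strongest reply is that the demonstration covers one answer pattern only. A patient who names a pen and ticks TRUE throughout scores exactly 8, so under a fixed mark one true statement marked FALSE means failure. Three true-keyed statements are worded negatively (Q3 items 3 and 4, Q4 item 4), so blanket agreement is not obviously the natural response. Nothing in the documents says how common it is. This stands, and it limits the claim.

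The planned output also gives some sight of the problem. The answer distributions in section 9.7.1 will show how many patients ticked TRUE on Q3 item 6, which is an upper bound on the all-TRUE share. Section 9.7.2 already describes success factors by paper and web. This stands too, but neither table changes who is counted as sufficiently understanding.

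A reader might infer that the factor cannot tell understanding from agreement at all, or that a high result carries no information. The documents do not support that: guessing and all-FALSE answering are screened out. Pass rates for partial agreement would need an assumed, constant chance of ticking TRUE on every item, and a choice between the fixed mark and the percentage.

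A reader might also infer that the HCP understanding factor has the same weakness. Its mark is "at least 11 correct or consistent answers out of 14 sub-questions". Agreeing with every statement and ticking every option gives 3 of 5 on Q3, 4 of 5 on Q4 and 3 of 4 on Q7, which is 10 of 14 and fails. An HCP who is all-TRUE on Q3 and Q4 reaches 11 only by answering Q7 fully to key (7 + 4), which means correctly leaving option 2 blank. That requires discrimination.

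**Conclusion.** The point holds for the patient factor. With one false-keyed statement in ten, uniform agreement passes in all three questionnaire paths and under both readings of the pass mark. This follows from the printed key, skip rules and cut-off, and needs no assumption. The bias is towards reaching 80%.

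Its size cannot be stated, because the share of all-TRUE responders is unknown. On the assumed pass rates above, between 20% and 50% of respondents would have to answer this way to lift the factor to the threshold. Factor 2 cannot produce a finding of effectiveness alone, since two of three factors are needed. The defect is a missing safeguard in the scoring. It does not show that the survey's result will be wrong.

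**What to change.** **Questionnaires already collected or in the field.** Under section 6, Wave 1 started in September 2019 and Wave 2 was scheduled from January 2020, so the primary definition should stay as it is. Beside factor 2, report the share of patients who ticked TRUE on every statement shown, overall and separately for web and paper. Add a sensitivity analysis, specified before the data are examined, in which factor 2 also requires Q3 item 6 to be answered FALSE, and state whether the 80% conclusion changes. This should remain a sensitivity analysis: it rests on a single item, and Q3 item 2 in the same list largely reveals that item's answer. It costs one extra table row and one alternative scoring rule.

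**Questionnaires still to be fielded.** If Wave 3 goes ahead (data collection planned from June 2021), reword statements so that at least three false-keyed ones, drawn from the patient guide, are among the items every respondent sees. Q4 items 2 and 3 should not be used for this, because the skip rules remove one of them for patients who name a pen. All-TRUE then scores at most 7 of 10 or 6 of 9 and fails in every path.

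**Cost.** The revised questionnaire must be translated again, factor 2 may come out lower, and Wave 3 results on this factor will not be directly comparable with earlier waves. The reports should say so.
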